1. LIST OF ABBREVIATIONS

ACT	Artemisinin-based combination therapy
AE	Adverse event
A/L	Artemether-Lumefantrine
ALT	Alanine Aminotransferase
AS	Artesunate
AST	Aspartate aminotransferase
CRF	Case Report Forms
CTCAE	Common terminology criteria for adverse events
CTSG	Clinical trials support group (MORU)
DHA	Dihydroartemisinin
DNA	Deoxyribonucleic Acid
DOT	Directly Observed Therapy
DRC	Democratic Republic of the Congo
DSMB	Data and Safety Monitoring Board
EDC	Electronic data capture
EDTA	Ethylene-diamine-tetra-acetic acid
GCP	Good Clinical Practice
GCS	Glasgow Coma Scale
Hb	Haemoglobin
Hct	Haematocrit
IM	Intramuscular
IRB	Institutional Review Board
IV	Intravenous
KIMORU	Kinshasa Medical-Oxford Research Unit
LDH	Lactate Dehydrogenase
MORU	Mahidol-Oxford Tropical Medicine Research Unit
NIMR	National Institute for Medical Research (Tanzania)
NMCP	National Malaria Control Programme
PI	Principal Investigator
PCR	Polymerase Chain Reaction
PCT	Parasite Clearance Time
QA	Quality Assurance
QC	Quality Control
RDT	Rapid Diagnostic Tests
SAE	Serious Adverse Event
SmPC	Summary of product characteristics
SOP	Standard Operating Procedure
SSIs	Semi-structured Interviews
SUSAR	Suspected unexpected severe adverse reaction
WHO	World Health Organisation

2. SYNOPSIS

Study Title	Convenience and cost-aspects of a new 1-step reconstitution injectable artesunate compared to conventional 2-step injectable artesunate for the treatment of severe falciparum malaria: a multi-centre study
ACRONYM	1STEP-AS
Trial Design	Individually-randomised controlled non-inferiority trial comparing 1-step parenteral artesunate vs conventional 2-step parenteral artesunate, with ancillary qualitative and cost-evaluation components
Trial Participants	
Part 1:
 
 Children with severe falciparum malaria admitted to hospital 
Part 2:
 
 Semi-structured Interviews (SSIs) with study staff, and other health staff who treat severe malaria patients SSIs with malaria policy makers and stakeholders
Sample size	
Part 1:
 
Total 200 participants. Estimated 100 per site.
 
 Korogwe District Hospital, Tanga, Tanzania (East Africa) Kinshasa Medical Oxford Research Unit, D.R. Congo (Central Africa) 
Part 2:
 
For both sites in total 40 SSIs with study staff, health staff, policy makers and stake holders; and survey/questionnaires with 150 health staff.

Inclusion Criteria	
Part 1:
 
 Male and female children aged >3months and <16 years. Clinical diagnosis of severe P. falciparum malaria; or parasitological confirmed P. falciparum hyperparasitaemia >350,000/ uL. Positive malaria test result, by rapid diagnostic test (RDT). Weight of 5 kg or greater. Written informed consent by the parent or guardian. 
Part 2:
 
Study staff and health staff
 
 Study staff who prepare and administer artesunate injection to patients in the study or health staff who have not administer the artesunate injection to patients in the study by themselves but are either aware of malaria treatment, artesunate injection, or have observed the treatment provided to severe malaria patients. Written informed consent by the study staff and health staff 
Study staff for a short video-record
 
 Study staff who would like to participate in the video record of a procedure to show how 1-step and 2-step artesunate injections are prepared and administered. Written informed consent by the study staff

	
Policymakers and stakeholders
 
 • Those who are working in the National Malaria Control Program (NMCP) or relevant organizations (WHO, INGOs/NGOs) within the country. • Written informed consent by the potential participant
Exclusion Criteria	
Part 1:
 
 • Participation in other intervention studies • Known allergy to artemisinin derivatives. • Known history of parenteral treatment for severe malaria for the current episode of illness before admission. Treatment before admission with an oral antimalarial drug (used for the treatment of uncomplicated malaria) or a single dose of pre-referral rectal artesunate are not exclusion criteria. 
Part 2:
 
Study staff and health staff; Policymakers and stakeholders; Study staff and health staff for a short video-record
 
 • Unwilling to participate in the study • Unable to communicate
Planned Trial Period	18 months, start in Q4 2021. (Estimated patient recruitment November 2021 – October 2022. Patient duration of participation 1 month.)
Co-Primary Objectives	
Assessment of:
 
 1. Convenience and rapidness of administration of 1-step vs. conventional 2-step parenteral artesunate formulations and 2. Costs of administration of 1-step vs. conventional 2-step parenteral artesunate formulations
Secondary Objective	1. To assess the acceptability, policy and implementation perspectives, and health care worker satisfaction regarding the use of 1-step formulation of parenteral artesunate..
Exploratory Objectives	
 1. To assess and compare P. falciparum parasite clearance rates of 1-step vs. conventional 2-step parenteral artesunate formulations. 2. To assess and compare time from intravenous treatment to follow up treatment with oral drugs with 1-step vs. conventional 2-step parenteral artesunate formulations. 3. To assess and compare disease outcome parameters between 1-step vs. conventional parenteral artesunate formulations. 4. To assess and compare adverse events between 1-step vs. conventional 2-step parenteral artesunate formulations.
Co-primary endpoints	
 1. Time to administration of treatment comparing 1-step vs. conventional 2-step parenteral artesunate formulations (by time-and-motion methods). 
and
 
 2. Costs of administration of 1-step vs. conventional 2-step parenteral artesunate formulations at health facility, and at health system level.

Secondary endpoint	1. A mixed method social science study will assess feasibility, practicability, and satisfaction of 1-step formulation of parenteral artesunate. (To include study staff, health staff, and policymakers and stakeholders.)
Exploratory endpoints	
 1. Parasite clearance half-life and other parasite clearance parameters (PC50, PC90, 12-hour parasite reduction ratio) compared between 1-step vs. conventional 2-step parenteral artesunate formulations. 2. Time from start parenteral treatment to follow up treatment with an oral ACT (recovery to per os treatment) of 1-step vs. conventional 2-step parenteral artesunate formulations. 3. Fever clearance time (i.e. the time taken for the tympanic temperature to fall below 37.5°C and remain there for at least 24 hours) of 1-step vs. conventional 2-step parenteral artesunate formulations. 4. Incidence of adverse events and serious adverse events by study arms within the first 28 days.
Drugs	
Artesunate (1-step parenteral) VERSUS Artesunate (conventional 2-step parenteral)
 
Then oral artemisinin combination therapy as follow-on treatment from parenteral treatment: artemether-lumefantrine (A/L), if available and no contraindication, otherwise other ACT. Rescue treatment: quinine.

3. BACKGROUND AND RATIONALE

3.1 Background

[figure not shown]
Parenteral artesunate is the first-line treatment for severe malaria.^{1,2} The two largest ever treatment trials conducted in patients hospitalised with severe malaria, which compared parenteral artesunate (produced by Guilin/ Fosun) with quinine: SEAQUAMAT in Asia in 1,461 patients³, and AQUAMAT in Africa in 5,425 children⁴. In both trials artesunate was associated with a significant and substantial reduction in mortality compared to quinine (a 34.7% relative reduction in deaths in SEAQUAMAT, 22.5% in AQUAMAT), which was not at the expense of an increase in severe sequelae. These findings resulted in a change of the WHO recommended first line antimalarial therapy for severe malaria in all endemic settings, and it has been estimated by the Medicines for Malaria Venture that since 2011 this has saved well over 500,000 young lives in Africa (<https://www.mmv.org/our-impact/achievements/168-million-vials-artesun-delivered-treat-children-severe-malaria>).

The conventional formulation of injectable artesunate requires a 2-step reconstitution and dilution of the artesunate hemisuccinate powder, including reconstitution in a sodium bicarbonate solution followed by further dilution in 5% dextrose or normal saline. The 2-step procedure takes time and is error prone, dissolving the artesunate powder in the bicarbonate solution is sometimes difficult, and the 2-step procedure requires additional consumables, like sterile syringes (<https://www.severemalaria.org/toolkits-training/injectable-artesunate-tools-training>). Preparation of conventional injectable artesunate (Artesun SmPC) requires shaking the vial for 3 to 5 minutes to mix well until the powder is completely dissolved and the solution is clear. Another disadvantage of the conventional artesunate is the two steps needed to reconstitute artesunate powder by sodium bicarbonate first then to dilute the solution by sodium chloride should not be exchanged. Otherwise, artesunate will not be dissolved. Such malpractice can cause a waste of medicine and put critical ill severe malaria patient under risk. 1-step artesunate can avoid such mistakes.⁵

For treatment of severe malaria, a medical emergency, this poses important disadvantages, in particular in under-resourced healthcare settings in Sub-Saharan Africa. A new formulation of injectable artesunate has been developed by Fosun Pharma requiring a simpler 1-step reconstitution. Bio-equivalence of the new formulation to the conventional formulation was shown in healthy volunteers led by [name], University of Oxford (report attached in Appendix 6). The summary of the results for artesunate and dihydroartemisinin were *“Parenteral administration of test and reference formulations showed matching exposures to the combined exposure to artesunate and dihydroartemisinin, and bioequivalence of the test formulation could be demonstrated both when administered IV (Table 3) and IM (Table 6)”*. The new formulation is currently awaiting WHO prequalification and is expected to be launched in 2022, “Argesun” WHO prequalification reference number MA168 ([name], Fosun Pharma, personal communication).⁶

The new 1-step artesunate parenteral formulation is thus expected to be equally effective, but likely more convenient and faster to use than conventional formulation. And to avoid reconstitution mistakes in field practice. Also, for the conventional formulation, the volumes of 0.9% sodium chloride used for IV route and IM route are different, for IV route: After reconstitution and dilution, one ml of solution for injection contains 10 mg artesunate. IM route: After reconstitution and dilution, one ml of solution for injection contains 10 mg artesunate. This can cause confusion among health workers and lead to mistakes. The 1-step formulation uses the same volume of solvent for IV and IM. In addition, the 1-step reconstitution is expected to be cheaper to administer, because it will use less of the health professional’s time and will use less consumables. We propose a study to compare and quantify convenience and costs of the new 1-step artesunate parenteral formulation versus the conventional formulation in a randomised study. This study will also integrate social science studies to explore and compare acceptability of 1 step artesunate with the conventional formulation using

SSIs and surveys among study staff, health staff and policymakers. In addition, efficacy data and adverse events will be captured.

3.2 Study Rationale

We seek to evaluate the practical benefits of the new formulation in a clinical trial supported by an ancillary social sciences study, and a cost analysis informed by the first two activities. The randomised study will formally compare between the two artesunate formulations: the speed and convenience of preparation and use, the costs of drug administration, basic pharmacodynamic measures and adverse events. A mixed method social science study will explore the opinion of healthcare workers regarding the use of the new artesunate formulation, including the policy and implementation perspectives from policymakers. Previous comparisons of artesunate suppositories and parenteral artesunate have reported parasite clearance times⁷ (<https://www.severemalaria.org>), and although both arms of the trial contain an identical active drug (artesunate) in the same dosages, we will also collect this information as a precaution to exclude the possibility of an unexpected, substantial difference in drug activity in patients with severe malaria.⁸

A feasibility assessment of injectable AS is important.⁹ Previous analyses have shown the mortality benefit and cost-effectiveness of reduced delays to effective treatment for severe malaria.^{10,11} Studies to evaluate new treatments for severe malaria should not only rely on efficacy (mortality) outcomes, but also include factors determining effectiveness under field conditions.¹² An important factor is the convenience to use the antimalarial drug. An objective measure of this is the time needed to correctly prepare the artesunate solution for injection, which will be evaluated in this study. In

addition, social science studies will explore the practicalities such as convenience, policy and implementation related issues and perceived benefits of using the new 1-step formulation compared to the conventional 2-step formulation.

Cost effectiveness of drug treatment for severe malaria is important and needs to be based on reliable evidence in the context of the high mortality caused by the disease.¹³ Previous assessments have shown that compared to parenteral quinine, AS is highly cost effective for the treatment for severe malaria in Asia and Africa.^{14,15} In the current study we will focus on the costs of the two different artesunate formulations and the consumables needed for their administration. These direct costs are important at the hospital level, but also for deployment in the wider health system. For example, for the public health system: the shipment cost for the 1-step artesunate will be cheaper than the cost for the conventional 2-step artesunate because the unit volume per pack (box) is smaller for the 1-step artesunate, and lighter.

The new formulation contains the same dose of active compound, artesunate, as the conventional formulation, and has shown bioequivalence in a comparative study in healthy subjects ([name], University of Oxford, personal communication). However, it has not been deployed, yet, for the treatment of severe malaria patients. Although not the primary goal of the study, we will accurately document efficacy, safety and tolerability outcomes using the new formulation. As an exploratory endpoint, these outcomes will be compared with the conventional artesunate formulation, since the study is not powered to compare these formally. Efficacy, safety and tolerability will be assessed through in-hospital monitoring of vital signs, physical examinations, blood smears, biochemistry assays and full blood counts. Adverse events will be recorded.¹⁶ As an important pharmacodynamic measure of the drug, parasite clearance dynamics will be assessed by repeated assessments of the parasite counts after the start of parenteral antimalarial treatment.¹⁷

The sites have been chosen based on their ability to recruit patients with severe malaria, presence of established clinical research programme, and the feasibility to perform the proposed research activities. They also represent large African countries, one French-speaking in Central Africa, and one English-speaking in East Africa, and both with a substantial burden of severe falciparum malaria. Moreover, advanced marketing authorisation has been approved in Tanzania and the DRC, and in two other countries, Malawi and The Gambia ([name], Fosun Pharma, personal communication).

All the organisations in this collaboration will work closely with local counterparts including the National Malaria Control Programmes (NMCPs), non-governmental and other relevant organisations. The sites have extensive experience of conducting trials of severe malaria.¹⁸ If 1-step parenteral AS is more feasible than the existing formulation, the study will facilitate the decision of countries whether to switch to the new formulation within a reasonable time frame.¹⁹

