2. GENERAL ANALYSIS APPROACH

The principle of intention to treat (ITT) will be the main strategy of analysis for the primary outcome. These analyses will be conducted on all patients assigned to the treatment groups as randomised. Any patients subsequently found not to be eligible during the trial or that did not receive a full course of study drug will be included in these analyses. Per Protocol (PP) analysis will be conducted to examine robustness of ITT results. This will be a form of sensitivity analysis to the intention to treatment analysis principle. In the PP analyses, all patients wrongly included in the study based on the inclusion/exclusion criteria will be excluded from analyses.

The cost analysis of 1-step parenteral AS will assess health facility-level costs, and health system costs to encompass all costs of a potential change from conventional to 1-step artesunate, including re-training, materials, drug replacement. Unit costs will be assigned to healthcare worker time spent on managing patients with severe malaria (derived from the time and motion surveys). Micro costing will be carried out in each of the sites to estimate the costs of equipment and consumables associated with provision of artesunate with each of the formulations. The resulting labour and consumable mean costs will be compared in patients treated with 1-step vs conventional artesunate formulation.

Time from opening box to completed preparation of syringe will be summarised using means and standard deviation for each each arm. Difference in means and the correponding 95% confidence intervals will be reported. We will provide overall comparisons by arm as well as for each site separately. The comparisons will be done for baseline times ans well as for all recorded times. Total cost of consumables in US dollars will be summarised in a similar way. A Student's independent t-test will be used for comparison of means between groups. The Central Limit Theorem justifies the use of the Student's t-test even if the times/costs may not be normally distributed because of the large sample size. However, if the data will be highly skewed, non-parametric tests such as Manny-Whitney (Wilcoxon) U test will be considered. Statistical significance will be declared at 5% significance level.

Data analysis will be performed using Stata 17 or higher, StataCorp, 4905 Lakeway Drive College Station, Texas 77845 USA

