1. Convenience and rapidness of administration of 1-step vs. conventional 2-step parenteral artesunate formulations
and
2. Costs of administration of 1-step vs. conventional 2-step parenteral artesunate formulations

Primary endpoint

1. Time to administration of treatment comparing 1-step vs. conventional 2-step parenteral artesunate formulations (by time-and-motion methods).
and
2. Costs of administration of 1-step vs. conventional 2-step parenteral artesunate formulations at health facility, and at health system level.

STATISTICAL ANALYSIS PLAN

Table 2 Drug preparation times

Time from opening box to completed preparation of syringe, at baseline only				
	Minutes and seconds, mean (SD)		Difference in means, (95% CI)	p-value
	1-STEP AS (N=XXX)	2-STEP AS (N=XXX)		
Overall	XX.X (XX.X)	XX.X (XX.X)	XX.X (XX.X - XX.X)	X.XXX
By site				
DRC	XX.X (XX.X)	XX.X (XX.X)	XX.X (XX.X - XX.X)	X.XXX
Tanzania	XX.X (XX.X)	XX.X (XX.X)	XX.X (XX.X - XX.X)	X.XXX
Time from opening box to completed preparation of syringe, at all recorded times.				
Overall	XX.X (XX.X)	XX.X (XX.X)	XX.X (XX.X - XX.X)	X.XXX
By site				
DRC	XX.X (XX.X)	XX.X (XX.X)	XX.X (XX.X - XX.X)	X.XXX
Tanzania	XX.X (XX.X)	XX.X (XX.X)	XX.X (XX.X - XX.X)	X.XXX
Total cost of consumables in US dollars, mean, SD.				
Overall	XX.X (XX.X)	XX.X (XX.X)	XX.X (XX.X - XX.X)	X.XXX
By site				
DRC	XX.X (XX.X)	XX.X (XX.X)	XX.X (XX.X - XX.X)	X.XXX
Tanzania	XX.X (XX.X)	XX.X (XX.X)	XX.X (XX.X - XX.X)	X.XXX

USD calculated from average cost of consumables used, and wastage of drug.

STATISTICAL ANALYSIS PLAN

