3.4 Fever clearance and parasite clearance during treatment, by treatment allocation

Table 4 Clinical recovery*, fever clearance, and parasite clearance by study arm**

	1-STEP AS N=XXX	2-STEP AS N=XXX	Both groups N=XXX	P- value (2-sided)
Hours to fever clearance, mean (SD) (baseline to start of first 24h period <37.5C; temperature was recorded every 4 hours, until day 2, then 6 hourly)				
DRC	XX.X (X.X)	XX.X (X.X)	XX.X (X.X)	X.XXX
Tanzania	XX.X (X.X)	XX.X (X.X)	XX.X (X.X)	X.XXX
All study sites	XX.X (X.X)	XX.X (X.X)	XX.X (X.X)	X.XXX
Day 3 blood smear still positive, n/N (%)** (taking prior clearance or discharge as negative)				
DRC	XX/XXX (XX)	XX/XXX (XX)	XX/XXX (XX)	X.XXX
Tanzania	XX/XXX (XX)	XX/XXX (XX)	XX/XXX (XX)	X.XXX
All study sites	XX/XXX (XX)	XX/XXX (XX)	XX/XXX (XX)	X.XXX
Hours to tolerate oral medication, mean (SD)* (baseline to start of oral ACT)				
DRC	XX/XXX (XX)	XX/XXX (XX)	XX/XXX (XX)	X.XXX
Tanzania	XX/XXX (XX)	XX/XXX (XX)	XX/XXX (XX)	X.XXX
All study sites	XX/XXX (XX)	XX/XXX (XX)	XX/XXX (XX)	X.XXX
Parasite clearance half-life in hours, mean (SD)** (excluding patients with initial count insufficient to estimate half-life)				
DRC	X.X (X.X)	X.X (X.X)	X.X (X.X)	X.XXX
Tanzania	X.X (X.X)	X.X (X.X)	X.X (X.X)	X.XXX
All study sites	X.X (X.X)	X.X (X.X)	X.X (X.X)	X.XXX

*Protocol recommends patients receive a minimum of 3 doses of injectable artesunate before switch to oral ACT. Patients may vary if discharged before 24 hours, died, or referred.

** Parasite dynamics will be affected by patients who are transfused.

STATISTICAL ANALYSIS PLAN
3.5 Safety assessments and tolerability (Incidence of adverse events and serious adverse events by study arms within the first 28 days)

Safety analyses will be based on the whole population that get administered the study drug. That is, the safety and tolerability data will be pooled from all the sites that received the same antimalarial treatment.

The safety and tolerability of 1-STEP AS versus 2-STEP AS will be assessed by comparing the frequency (%) of adverse events and serious adverse events, with particular attention to the variables listed below, which pertain to severe malaria.

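### SAP Table 4 compares arms on clearance and recovery by a two-sided p-value alone, which cannot exclude a substantial difference in activity; it needs a difference with a 95% CI

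*Protocol*

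**What the plan says.** Protocol 3.2 (Study Rationale) says clearance information is gathered "as a precaution to exclude the possibility of an unexpected, substantial difference in drug activity" between the two products in severe malaria. The same section lists what the randomised study will formally compare, including "the costs of drug administration, basic pharmacodynamic measures and adverse events". It later calls the efficacy, safety and tolerability comparisons exploratory, "since the study is not powered to compare these formally". Protocol 4.3 and 5.4.3 also class them as exploratory, whereas SAP 2.1.3 lists them as secondary.

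SAP 3.4, Table 4 has columns for each arm, a pooled Both groups column, and one comparison column headed "P- value (2-sided"). Rows hold means with SDs or counts with percentages, by site and overall. The half-life row carries the note "excluding patients with initial count insufficient to estimate half-life".

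For preparation time the SAP plans more. Its General Analysis Approach says "Difference in means and the correponding 95% confidence intervals will be reported", with consumables cost handled likewise, and Table 2 has a column for it: "Difference in means, (95% CI"). The only decision rule in the SAP is significance at the 5% level. Protocol 9.2.2 and 9.2.3 mention 95% intervals for crude proportions and for group means, where relevant or appropriate, but not for a difference between arms. Neither document says what would count as substantial.

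**The concern.** Excluding a difference means showing that the data are incompatible with values beyond some size, and that takes an interval. A p-value above 0.05 says only that zero is not ruled out. The two coincide least when a comparison has limited power, which is how the protocol describes this one.

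The precaution has a purpose. Protocol 3.2 says the new formulation had not yet been used in patients with severe malaria. In the appended pharmacokinetic report (Appendix 5), intravenous artesunate Cmax missed the bioequivalence criterion (ratio 81.50%, 90% CI 74.74 to 88.87), and the lower limit for AUC to last observation was 80.09 against a bound of 80. The costing (Protocol section 6, Part 3) also takes as a working assumption that clinical outcomes do not differ. If Table 4 is completed as laid out, the report will not show how large a loss of activity remains compatible with the data.

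**Working it through.** **The plan's own figure.** The only sample-size calculation (Protocol 9.1; SAP 2.2.1) concerns preparation time: margin 1 minute, SD 2 minutes, one-sided alpha 0.025, power 90%.

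- n per arm = 2 × (1.960 + 1.282)² × 2² / 1² = 84.06, rounded up to 85.
- With 15% loss: 85 / 0.85 = 100 per arm.

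Both figures reproduce. No margin, SD or power is given for any Table 4 outcome.

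**What a non-significant result leaves open.** The documents give no half-life SD, so differences are in SD units. SE = √(2/n), which is 0.1414 at n = 100 per arm. A two-sided p-value with 198 degrees of freedom then implies:

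- p = 0.10: difference = 1.653 × 0.1414 = 0.234; 95% CI = 0.234 ± 1.972 × 0.1414 = -0.045 to 0.513.
- p = 0.50: difference 0.096; 95% CI -0.183 to 0.374.

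Both results would be called non-significant. The second excludes a 0.5 SD difference and the first does not.

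**Precision and chance of a non-significant result.** Formulas:

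- Half-width of the 95% CI = t(0.975, 2n-2) × √(2/n).
- Chance of p > 0.05 when the true difference is d = 1 - Φ(d/√(2/n) - 1.96).
- Chance that the 95% CI lies wholly inside ±0.5 SD when there is no true difference = 2Φ(0.5/√(2/n) - 1.96) - 1.

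| n per arm | Half-width (SD) | p>0.05 if d=0.3 | if d=0.4 | if d=0.5 | CI inside ±0.5 SD if d=0 |
|---|---|---|---|---|---|
| 100 (all randomised) | 0.279 | 0.436 | 0.193 | 0.058 | 0.885 |
| 85 (after 15% loss) | 0.303 | 0.502 | 0.259 | 0.097 | 0.806 |
| 50 (about one site) | 0.397 | 0.677 | 0.484 | 0.295 | 0.411 |

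The difference detectable with 80% power at 100 per arm is (1.96 + 0.842) × 0.1414 = 0.396 SD.

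**The half-life subset.** The number excluded for a low initial count is not given. If 60 per arm were evaluable (an assumption), the half-width would be 1.96 × √(2/60) = 0.358 SD.

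**In hours.** Assuming a half-life SD of 0.5 to 1.5 h, the half-width at 100 per arm is 0.14 to 0.42 h. The upper limit in the p = 0.10 example is 0.513 × 0.5 = 0.26 h to 0.513 × 1.5 = 0.77 h.

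**The case against.** The strongest reply has four parts.

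- **Table 4 is not bare.** Someone might infer that it reports p-values and nothing else. It does not: it gives arm means with SDs, or counts with percentages, so a reader can subtract and approximate an interval. That stands, except that the half-life row omits patients and the template shows no n for it. Table 4 is also a partial shell: PC50, PC90 and the 12-hour reduction ratio are listed endpoints without a row. A missing column is therefore not proof that no interval will ever appear, but nothing elsewhere in the documents commits to one for the difference.
- **The outcomes are labelled exploratory and unpowered.** This lowers the stakes. It does not rescue the p-value, because low power is where non-significance says least. The secondary label in the SAP and the promise in Protocol 3.2 to compare pharmacodynamic measures formally pull the other way.
- **A large difference would probably be detected.** At 100 per arm a true 0.5 SD difference gives p < 0.05 in about 94% of trials (1 - 0.058). That is a fair point about the design. It does not tell the reader of one particular non-significant result what has been excluded.
- **Equivalence was addressed in the pharmacokinetic study.** Dihydroartemisinin and combined exposure met the criteria by both routes, so Appendix 5 is no evidence of lost activity. But that study was in healthy volunteers, and the protocol collects clearance data in patients as an additional check.

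A reader might also infer that the investigators will treat a non-significant half-life comparison as proof of no difference. Neither document says so, and the protocol's statement about power points towards caution.

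**Conclusion.** The point holds as a mismatch between a stated purpose and a planned output. Table 4's sole between-arm measure cannot exclude a substantial difference, and no margin or between-arm interval for these outcomes is specified anywhere. At 100 per arm a result of p = 0.10 leaves differences up to about 0.51 SD open, and a true 0.40 SD difference gives p > 0.05 in about 20% of trials.

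These figures assume roughly normal outcomes, equal SDs and full evaluability. The conversion to hours and the 60-per-arm case rest on assumed values.

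The documents do not support inferring that the trial is too small for the purpose. With no true difference, the 95% CI at 100 per arm would fall inside ±0.5 SD with probability about 0.89, so an interval could meet the protocol's aim if a limit of that order were judged acceptable. For ±0.3 SD the probability is only 0.13, so the limit has to be stated. The co-primary endpoints and the sample size are unaffected. This is a reporting change that should be made, of moderate weight.

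**What to change.** In SAP Table 4, keep the Both groups column and add:

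1. The 1-step minus 2-step difference with its 95% CI, in the format of Table 2, using a risk difference for the day-3 smear.
2. The evaluable n by arm for each row, above all for half-life.

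In the text of SAP 3.4, state before analysis what size of difference counts as substantial for each outcome, or at least for half-life, and say that the conclusion will be read from the interval rather than the p-value. A ratio of geometric means for half-life and an estimate stratified by site are optional refinements.

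The cost is one extra column, the n entries and a little analysis work on outcomes the protocol calls exploratory. Agreeing on the limit takes some clinical discussion. No new data and no change in sample size are needed.
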